Assessment Procedures. Following informed consent, eligible participants will complete a breathalyzer or saliva alcohol test, urine drug screen, blood draw, and pregnancy test (for women). Participants will have the option to participate in genomic research by providing an extra 7 milliliters of blood during the study blood draw. Participants will complete a psychosocial and medical history assessment (see Table 2). Note that for telehealth participants, biological specimens will not be collected, however, female participants will be required to take a pregnancy test (provided by study staff) and will be required to verbally confirm a negative result prior to continuing with any procedures. Provided that all inclusion and exclusion criteria are met, participants will be scheduled to complete the laboratory testing portion of the study.

Participants will be instructed to abstain from caffeine, nicotine, alcohol or other substances of abuse prior to the laboratory testing procedure. Smokers will be asked to abstain from smoking during study procedures and offered a nicotine patch prior to participation. Nicotine patch dosage will be determined by the number of cigarettes participants smoke daily (≥ 20 cigarettes/day=21mg; 10–19 cigarettes/day = 14 mg patch; 5–9 cigarettes/day = 7 mg patch).

Human Laboratory Procedure. Participants will complete an alcohol cue reactivity task and the TAP procedure approximately 45 minutes after receiving a 40 IU intranasal dose of oxytocin or placebo (i.e., saline). In a recent review of oxytocin studies, 40 IU is within the normal dosing range for humans and is one of the most common single dose concentrations utilized in human research⁷⁸. This literature indicates that a 40 IU dose is safe and effective in eliciting effects on HPA axis reactivity among participants with AUD^{78,79}.

Alcohol Cue Procedure. Consistent with the procedure developed by Monti and colleagues⁸¹, participants will spend 3 minutes holding and smelling a control beverage (water), and reactivity (e.g., craving, urge to use) will be assessed. Following a 3-minute rest period, participants' preferred alcoholic beverage will be presented and poured into an appropriate glass

and they will spend 3 minutes holding and smelling the beverage. Subjective and physiological reactivity will be measured again.

TABLE 2. ASSESSMENT MEASURES

Construct	Measure

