At the outset of the TAP procedure, the words "Get Ready" appear on the computer screen in front of the participant. Then the words "Press the Spacebar" appear on the screen. Participants press and hold the space bar until the words "Release the Spacebar" appear on the screen, at which time the participant will release the spacebar as quickly as possible. A "win" is indicated to the participant with the words "You Won. You May Give a Shock" appearing on the screen.

Following a winning trial, participants choose whether or not to shock their opponent and its intensity on a level ranging from 1 (very mild shock, definitely not painful) through 10 (intense shock, definitely painful). A “loss” is indicated with the words “You Lost. You Will Get a Shock” appearing on the screen. The shock intensity received by the participant is randomly selected by the computer software within the calibrated range specified for each participant.

Calibration: The finger stimulator apparatus (Colbourn Instruments, Whitehall, PA) is calibrated for each participant, controlling for individual differences in pain threshold that may influence shock selection. Two electrodes are attached to the participant’s middle and index finger on the non-dominant hand. Each participant is administered 1-second shocks that increase stepwise beginning with the lowest possible intensity. Participants are instructed to inform the researcher when the shocks are first detectable and then again when they experience a shock as painful. During the actual TAP procedure, shock levels range from 1 to 10 and correspond to the participant’s 55% through 100% pain threshold.

TABLE 3. LABORATORY TESTING

Duration	Procedure
Screening portion	
2-2.5 hours	Informed consent and assessment battery
30 minutes	Blood draw from nurse from Research Nexus
Laboratory portion	
Minute 0	Baseline measurement #1 (VAS, HR, BP, cortisol)
Minute 5	Baseline measurement #2 (VAS, HR, BP, cortisol)
Minute 10	Oxytocin or placebo administered
Minute 40	Post-medication assessment (VAS, HR, BP, cortisol)
Minute 45	Alcohol Cue
Minute 50	Post-Cue assessment (VAS, HR, BP, cortisol)
Minute 65	TAP
Minute 70	Immediate post-task assessment (VAS, HR, BP, cortisol)
Minute 85	15-minute post-task assessment (VAS, HR, BP, cortisol)
Minute 100	30-minute post-task assessment (VAS, HR, BP, cortisol)
Minute 130	60-minute post-task assessment (VAS, HR, BP, cortisol)
Minute 135	Participant debriefed, compensated and discharged

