12.0 Data Management and Statistical Analysis Plan

Descriptive statistics will be used to characterize participants at each time point. Because the units of randomizations are dyads (i.e., couples), all analyses will account for potential within-dyad correlation (e.g., intraclass correlation [ICC]). Generalized linear mixed models (GLMMs) with random couple effects will be used to assess group differences in baseline characteristics. These can be operationalized using SAS Proc Mixed and Proc GLIMMIX. Should any variables

exhibit significant departures from normality, variable transformations (e.g., logarithmic) or non-parametric approaches will be used, as appropriate. GLMMs are ideal for handling analyses involving correlated measures¹⁰⁸, and they will allow us to estimate both the between- and within-couple variation. GLMMs are also useful for modeling longitudinal (repeated) outcomes on individual subjects, and the models can be adapted with appropriate link functions for continuous, binary, and count outcomes. GLMMs will be constructed for analyses involving group (or subgroup) comparisons over time. The models will also control for relevant covariates, including baseline outcome levels and number of standard drinks during the 60 days prior to participation. Various covariance structures (e.g., compound symmetry, autoregressive, etc.) will be tested, with final model selection based on fit statistics such as Akaike Information Criterion¹⁰⁹. Analyses will be conducted using SAS v9.4 (Cary, NC).

Hypothesis 1: Participants who receive oxytocin, as compared to placebo, will demonstrate significantly lower craving, aggression, physiological (HR, BP), and neuroendocrine (cortisol) reactivity to the TAP. To test this hypothesis, GLMMs with identity link functions (for continuous measures) and log link functions (for count data) will be used to model the between-group differences. Random couple effects will be used to account for within-couple correlation.

Hypothesis 2: Oxytocin response will be greater among women as compared to men. To test this hypothesis, GLMMs will be used to assess serially measured time points following medication administration (15, 30, and 60 minutes post task). The effects of gender, time, and their interaction will be assessed. Primary outcomes include alcohol craving, aggression, and cortisol.

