Hypothesis 3: Oxytocin response will be lower among individuals with higher endogenous oxytocin levels and greater IPA severity. To test this hypothesis, alcohol craving, aggression, and cortisol levels will be examined as repeated measures variables using the strategies described above. Separate models will be conducted for endogenous oxytocin levels and IPA severity.

Randomization. Participants will be randomized to oxytocin or placebo. Because the extant literature suggests that the frequency and intensity of aggression in the TAP may be higher in men, on average, than women, a stratified randomization scheme will be used to ensure that groups are balanced by gender.

Sample Size Justification. Given the preliminary nature of this investigation, we aim to detect between-group differences in aggression measured by the TAP (oxytocin vs. placebo). Prior work¹¹⁰⁻¹¹² suggests that mean baseline aggression as measured within the TAP ranges from 2 to 4, with a standard deviation of 1.1 and with men having higher scores, on average, than women. With 50 couples (n=100) per group (and assuming alpha=0.05 and 2-sided hypothesis testing), we will have 80% power to detect moderate within-group changes (around 0.4 units [$\pm 10\%-20\%$] on the TAP shock intensity scale), consistent with our study hypotheses. We will have 80% power to detect moderate between-group differences (0.4 units) but with a larger alpha level (0.25), which is consistent with our pilot study framework.

Confidentiality and Data Security. All research personnel will attend a required in-service training conducted by [name] and [name] where the screening, informed consent, and assessment protocols will be described. The study protocol and safety plan will be printed and kept in a central location within the research space for easy access for all research staff. Standard operating procedures (SOPs) for the management of any participant or study-related emergency will be established and research staff will be trained on these protocols. All participant assessments will be scheduled during normal working hours beginning at 8am on the MUSC campus to ensure the presence of clinical staff and the safety of participants and

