(8) For studies in which alcohol is administered, the DSM plan must indicate that NIAAA guidelines for the administration of alcohol will be followed. These guidelines can be found at the following web address: <http://www.niaaa.nih.gov/research/guidelines-and-resources/administering-alcohol-human-studies>.

The proposed study does not involve alcohol administration.

(9) If the study has a follow-up phase, there must be a specific plan for referral to treatment during follow-up of any patient requiring additional intervention due to significantly increased alcohol consumption or serious psychiatric/medical symptoms.

The proposed study takes place during one study visit and does not include a follow-up phase. All participants will be provided with a list of community resources upon study completion. Ineligible individuals presenting with serious mental or physical health symptoms including acute alcohol withdrawal will be referred clinically.

(10) The DSM plan must indicate that all adverse events and unanticipated problems during follow-up will be reported (SAEs within 48 hours) to the IRB and NIAAA.

Not applicable, as the proposed study does not include a follow-up phase.

(11) The DSM plan must briefly describe the procedures for data quality assurance and confidentiality.

A data analytic plan is outlined in the Data Analysis section. Because this study is a preliminary test of a new medication, we are interested in examining a broad range of outcome variables. The main outcome variables include alcohol craving, aggression, and subjective, physiological, and neuroendocrine reactivity to the laboratory procedure. Outcome data will be analyzed using chi-square, ANCOVA, and Poisson regression models. The alpha level for statistical significance will be set at .05.

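### The only 80% power claim at alpha 0.05 is for a within-group change in TAP aggression, which cannot be observed because the TAP is run once, after dosing

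*Combined protocol and SAP*

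**What the plan says.** The Sample Size Justification (section 12.0) opens with a between-group aim: "we aim to detect between-group differences in aggression measured by the TAP (oxytocin vs. placebo". For 50 couples (100 participants) per group at two-sided alpha 0.05, it then says "we will have 80% power to detect moderate within-group changes", sized at about 0.4 units on the TAP shock intensity scale. The between-group contrast comes next, at a different level: "We will have 80% power to detect moderate between-group differences (0.4 units) but with a larger alpha level (0.25". The reason given is the pilot nature of the study. The inputs are an SD of 1.1 and prior-work means of 2 to 4. There is no SD of change and no partner ICC.

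On the schedule, section 10.0 says "Participants will complete an alcohol cue reactivity task and the TAP procedure approximately 45 minutes after receiving a 40 IU intranasal dose". In Table 3 the Minute 10 entry is "Oxytocin or placebo administered" and the only TAP entry is Minute 65. Both pre-dose baselines and every later assessment consist of VAS, HR, BP and cortisol. Section 13.0, item 9, adds: "The proposed study takes place during one study visit and does not include a follow-up phase".

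On the analysis, section 12.0 says "The models will also control for relevant covariates, including baseline outcome levels and number of standard drinks during the 60 days prior", with no exception for TAP aggression. Section 13.0, item 11, says of the outcome analyses: "The alpha level for statistical significance will be set at .05".

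**The concern.** A power statement should describe a quantity that the trial will measure and a test that it will run. This one describes a change from before to after dosing in a score that is taken only after dosing. It also departs from the aim stated just before it and from Hypothesis 1, both of which compare oxytocin with placebo.

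The pairing readers look for, 80% power at alpha 0.05 for 0.4 units, is thus attached to something unobservable. For the comparison that matters, the plan gives no power at the significance level set in section 13.0. A null between-group result could then be read as stronger evidence against an effect of 0.4 units than the design can supply. A related gap is that baseline adjustment cannot be carried out for TAP aggression as written, which leaves an undocumented modelling choice on an outcome that section 12.0 lists as primary.

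**Working it through.** **1. Can the change be observed?** Going through Table 3 in order:
- Minutes 0 and 5: VAS, HR, BP, cortisol.
- Minute 10: dose.
- Minute 40: VAS, HR, BP, cortisol.
- Minutes 45 and 50: alcohol cue and post-cue assessment.
- Minute 65: TAP.
- Minutes 70, 85, 100 and 130: VAS, HR, BP, cortisol.

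The screening portion of Table 3 and the assessment measures in Table 2 contain no TAP. Shock calibration measures detection and pain thresholds, not aggression. The within-subject comparison described in section 2.0 covers subjective, physiological and neuroendocrine responses and does not name TAP aggression. Participants with a pre-to-post TAP change: 0 of 200.

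**2. The plan's within-group figure.** Power = Φ(0.4 / (SD of change / √n) − 1.960). The SD of change is not given, so the 80% cannot be reproduced from the stated inputs. Taking it as 1.1 (a pre/post correlation of 0.5) with n = 100: 0.4 / 0.11 = 3.636, and Φ(3.636 − 1.960) = 95%. To get 80% needs either
- an SD of change of 0.4 × 10 / (1.960 + 0.842) = 1.43, or
- an SD of 1.1 with an effective n of (1.1 × 2.802 / 0.4)² ≈ 59, which is a partner ICC of 100/59.4 − 1 ≈ 0.68.

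**3. The between-group comparison.** Section 12.0 names couples as the unit of randomisation. The variance of a couple mean is 1.1² × (1 + ICC)/2, so with 50 couples per group

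SE = √(2 × 1.21 × (1 + ICC) / (2 × 50)).

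Power = Φ(0.4/SE − z), with z = 1.960 at alpha 0.05 and 1.150 at alpha 0.25. The difference detectable with 80% power at 0.05 is (1.960 + 0.842) × SE.

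| Assumed ICC | SE | Power, alpha 0.05 | Power, alpha 0.25 | Detectable difference, alpha 0.05 |
|---|---|---|---|---|
| 0 | 0.1556 | 73% | 92% | 0.44 |
| 0.2 | 0.1704 | 65% | 88% | 0.48 |
| 0.5 | 0.1905 | 56% | 83% | 0.53 |
| 1 | 0.2200 | 44% | 75% | 0.62 |

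A t test on 98 degrees of freedom gives slightly less at 0.05: 72%, 64%, 55% and 44%.

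**4. Reconciling the plan's two 80% figures.** The between-group 80% at alpha 0.25 is reached exactly at an ICC of about 0.67. That is close to the 0.68 in step 2, so both figures fit a single unstated assumption: an ICC near 0.67 with 1.1 as the SD of change. At that ICC, between-group power at alpha 0.05 is about 51%.

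**The case against.** **Little consequence.** The within-group sentence drives none of the planned hypothesis tests, the next sentence discloses alpha 0.25 with a reason, and the randomised comparison is intact. This is fair as far as it goes. At alpha 0.25 the 80% claim is met for any ICC up to about 0.67. But disclosing a lenient alpha does not make the other quantity measurable, and section 13.0 still sets .05.

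**Other readings of change.** Hypothesis 3 calls aggression a repeated measure, and the single TAP has 30 trials with a first unprovoked shock, so a within-task change could be computed. It would lie wholly after the dose, is not a defined outcome, and would not isolate a drug effect within a group. The repeated-measures wording itself conflicts with the schedule.

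**The power figures are conditional.** This stands. They assume an unadjusted comparison. Covariates explaining about 16% of the variance at ICC 0, or about 30% at ICC 0.2, would restore 80%, but the plan claims no such gain and no TAP baseline exists to supply it. They also assume that couples are randomised. The Randomization paragraph speaks of participants, and if partners were allocated independently, power at 0.05 would rise with ICC (about 75% at 0.2, 80% at 0.4). Section 12.0, however, names dyads as the randomised unit and counts 50 couples per group.

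**Covariates and visits.** The covariate sentence says relevant covariates and can be read as applying only where a baseline exists; a clarification is enough. The one-visit statement is weak support, because screening precedes a separately scheduled laboratory session. The conclusion rests on Table 3.

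**Conclusion.** The concern holds. The plan's only claim of 80% power at two-sided alpha 0.05 is for a TAP change that no participant can contribute to. For the comparison the plan names as its aim, power at 0.05 for 0.4 units lies between 73% (ICC 0) and 44% (ICC 1), below 80% across the whole of that range. The difference detectable with 80% power runs from 0.44 to 0.62 units. These figures rest on SD 1.1, 50 couples per group, couples as the randomised unit, no loss of participants and no gain from covariates. The ICC values are assumed. The randomised comparison stays valid; what is wrong is the stated justification for its size. This should be fixed, but it does not undermine the design.

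**What to change.** In the Sample Size Justification, delete the within-group power statement and give power only for the between-group difference in average shock intensity, with the assumed partner ICC. Reconcile the 0.25 there with the .05 in section 13.0 so that one alpha governs this test, and report power at the .05 already set for the outcome analyses. If the sponsor intends 0.25 as the decision level, both sections must say so. Possible wording:

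> With 50 couples (100 participants) per group, SD 1.1, two-sided alpha 0.05 and an assumed partner ICC of 0.2, power for a between-group difference of 0.4 units is 65%; 80% power corresponds to a difference of 0.48 units.

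In the analysis text of section 12.0, limit baseline adjustment to outcomes measured before dosing (VAS craving, HR, BP, cortisol). For TAP aggression, adjust for gender, which is already the stratification factor. This settles the model but should not be expected to add much power, since a mixed-sex couple randomised together is already balanced on gender.

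The cost is protocol and SAP wording only, with no added task, visit or participant. The sample stays at 100 couples, with its power correctly described.

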13.0 Provisions to Monitor the Data to Ensure the Safety of Subjects

Data and Safety Monitoring Plan. This section is based on the recommendations in NIAAA's "Data and Safety Monitoring Guidelines": <http://www.niaaa.nih.gov/ResearchInformation/ExtramuralResearch/ResourcesAppGrantees/guidelines.htm>.

Summary of the Protocol. The proposed study will examine the ability of oxytocin to reduce alcohol craving and aggression among individuals with a substance use disorder and co-occurring intimate partner aggression (IPA), and identify predictors of oxytocin response (e.g., gender, endogenous oxytocin, IPA severity). The primary outcomes in this study include a reduction in (1) alcohol craving, (2) aggression, and (3) subjective, physiological, and neuroendocrine reactivity to a laboratory task (i.e., modified Taylor Aggression Paradigm).

Trial Management. [name] (PI) will be responsible for monitoring the study. The study will be managed from the Addiction Sciences Division within the Department of Psychiatry and Behavioral Sciences at the Medical University of South Carolina (MUSC), College of Medicine, Charleston, SC.

Regulatory Issues.

- (1) The DSM plan must designate an experienced, qualified professional (usually the PI) who can distinguish a serious adverse event (SAE) from a non-serious adverse event (AE) and an unanticipated problem.

Drs. [name] (PI) and [name] (primary mentor) will be responsible for distinguishing between serious (SAEs) and non-serious adverse events (AEs), and determining study relatedness. Potential AEs and SAEs will be identified during the study via self-report data, as well as assessments and interviews. All unexpected AEs and SAEs will be monitored until resolved. A detailed summary of all AEs will be prepared weekly by the research staff and reviewed by the PI at the weekly study team meeting.

An Adverse Event (AE) is defined as any unwanted change, physically, psychologically or behaviorally, that occurs in a study participant during the course of the study that may or may not be related to study participation. AEs are reportable if the AE is unexpected AND related or possibly related AND serious or more prevalent than expected. The IRB definition of unexpected is that the AE is not identified in nature, severity or frequency in the current protocol, informed consent, investigator brochure or with other current risk information. The definition of related is that there is a reasonable possibility that the adverse event may have been caused by the drug, device or intervention. All AEs are reviewed weekly by the PI, and annually by the Data and Safety Monitoring Board (DSMB), MUSC IRB, and VA R&D. A Serious Adverse Event (SAE) is defined as an adverse event that has one of the following outcomes: results in death, is life-threatening, requires inpatient hospitalization or

prolongation of existing hospitalization, results in persistent or significant disability/incapacity, is a congenital anomaly/birth defect, OR requires intervention to prevent one of the above outcomes.

(2) This experienced, qualified professional may be the PI, an independent investigator, or a team of experts.

[name] (PI) will consult with [name] (Primary Mentor) to identify and determine AE severity.

(3) The DSM plan must indicate that serious adverse events and unanticipated problems will be reported to the local IRB, VA R&D, and to the NIAAA project officer within 48 hours.

AEs and SAEs occurring during the course of the trial will be collected, documented, and reported in accordance with protocol and IRB reporting requirements. Adverse Events (AEs) that meet criteria for reportable AEs will be reported to all regulatory entities including the local IRB, VA R&D, and NIAAA project officer within 48 hours. SAEs will be reported within 24 hours. All research staff involved with adverse event reporting will receive training including identification, evaluation, and documentation and reporting.

(4) The DSM plan must indicate that an annual report will be submitted to the NIAAA Project Officer summarizing all adverse events.

An annual report of all adverse events will be submitted annual to the NIAAA Project Officer. In addition, AEs will be reviewed weekly by [name], and annually by the Data Safety Monitoring Board (DSMB) and local IRB. Any significant actions taken by the local IRB, VA R&D, and protocol changes will be reported to NIAAA.

(5) The DSM plan must specify that female subjects who are pregnant, nursing, or not using effective methods of birth control will be excluded from studies involving the administration of alcohol and/or drugs.

The proposed study does not involve alcohol or drug administration. However, women who are pregnant or breastfeeding are not eligible to participate in the proposed study due to the known effects of the study drug (oxytocin) on parturition and lactation.

(6) The DSM plan must indicate that trained personnel will be present or on call when human laboratory studies of alcohol or other drug intake are conducted.

[name] (PI) and/or [name] (primary mentor) will be present or on call at the time of all study visits including the human laboratory visit.

(7) The DSM plan must indicate the follow up plans for serious adverse events and unanticipated problems.

For any SAE, the appropriate SAE protocol specific reporting forms will be completed and disseminated to the appropriate persons and within the designated timeframes as indicated above. If complete information is not available when the initial 24-hours that the SAE report is disseminated, follow-up information will be gathered to enable a complete assessment and outcome of the event. This information may include hospital discharge records, autopsy

reports, clinic records, etc. The research staff will attach copies of source documents to the SAE report for review by [name] and for forwarding to the NIAAA Program Officer. In addition, the PI will provide a signed, dated SAE summary report, which will be sent to the NIAAA Medical Safety Officer within 2 weeks of the initial SAE report. Follow-up of all unexpected and serious AEs will be reported to all regulatory entities including the local IRB, DSMB, and NIAAA. For each AE/SAE recorded, the research staff will follow the AE/SAE until resolution, stabilization, or until the subject is no longer in the study.

(8) For studies in which alcohol is administered, the DSM plan must indicate that NIAAA guidelines for the administration of alcohol will be followed. These guidelines can be found at the following web address: <http://www.niaaa.nih.gov/research/guidelines-and-resources/administering-alcohol-human-studies>.

The proposed study does not involve alcohol administration.

(9) If the study has a follow-up phase, there must be a specific plan for referral to treatment during follow-up of any patient requiring additional intervention due to significantly increased alcohol consumption or serious psychiatric/medical symptoms.

The proposed study takes place during one study visit and does not include a follow-up phase. All participants will be provided with a list of community resources upon study completion. Ineligible individuals presenting with serious mental or physical health symptoms including acute alcohol withdrawal will be referred clinically.

(10) The DSM plan must indicate that all adverse events and unanticipated problems during follow-up will be reported (SAEs within 48 hours) to the IRB and NIAAA.

Not applicable, as the proposed study does not include a follow-up phase.

(11) The DSM plan must briefly describe the procedures for data quality assurance and confidentiality.

A data analytic plan is outlined in the Data Analysis section. Because this study is a preliminary test of a new medication, we are interested in examining a broad range of outcome variables. The main outcome variables include alcohol craving, aggression, and subjective, physiological, and neuroendocrine reactivity to the laboratory procedure. Outcome data will be analyzed using chi-square, ANCOVA, and Poisson regression models. The alpha level for statistical significance will be set at .05.

Data quality will be monitored by random inspection of completed assessment forms by research staff. [name] and a statistician will examine the outcomes database for missing data, unexpected distributions or responses, and outliers. Any problems with the assessment process, data collection, or data entry will be discussed between [name]. Study procedures will follow the FDA's Good Clinical Practice Guidelines (www.fda.gov/oc/gcp). Confidentiality will be maintained during all phases of the study. Any outside requests for information or any breaches in confidentiality will be reported to [name]. All requests by subject's physicians and other medical providers will be referred directly to applicant. No names or other identifying information will be included on any source documents. Only a subject identification number will be used on source documents. All data will be kept securely in a locked cabinet in a locked office.

(12) Phase III clinical trials must have an independent data and safety monitoring board. Phase I and II studies that have multiple clinical sites, are blinded or employ particularly high risk interventions or vulnerable subjects may require a DSMB at the discretion of NIAAA.

The proposed study meets the definition of a phase II clinical trial in that (a) oxytocin has an established dosing range, (b) it will be conducted among 100-300 individuals, and (c) examines efficacy of oxytocin for a specific purpose (e.g., to reduce alcohol craving and IPA). We will create a DSMB to monitor overall participant safety, the rate and severity of adverse events, and the validity and integrity of the data. The panel includes 2 researchers with experience in treating patients with alcohol use disorders and IPA and a statistician. The board may be called at any point if needed for unexpected AEs, etc. Modifications will be made in the procedures and/or the protocol if necessary based on the recommendations of the board. A DSMB report will be filed with the IRB on a yearly basis, unless greater than expected problems occur. The report will include subject characteristics, retention and disposition of study subjects, quality assurance issues and reports of AEs, significant/unexpected AEs and serious AEs. Results will be reported at the end of the trial.

ClinicalTrials.gov Requirements: In accordance with Public Law 110-85, the proposed trial will be registered with ClinicalTrials.gov. Applicable requirements regarding results reporting will be adhered to.

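### Section 13.0 item (11) lists outcome analyses with no couple term, in conflict with the couple-level mixed models of Section 12.0; used in standard form with couples randomised, they would understate the standard error

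*Combined protocol and SAP*

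**What the plan says.** Section 12.0 (Data Management and Statistical Analysis Plan) sets a general rule: "Because the units of randomizations are dyads (i.e., couples), all analyses will account for potential within-dyad correlation". Under Hypothesis 1 it names the models: "GLMMs with identity link functions (for continuous measures) and log link functions (for count data) will be used to model the between-group differences". It then adds: "Random couple effects will be used to account for within-couple correlation". Hypothesis 2 uses the serial post-task readings, and Hypothesis 3 treats craving, aggression and cortisol as repeated measures under the same strategies.

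Section 13.0, item (11) of the Data and Safety Monitoring Plan, answers a prompt about data quality assurance and confidentiality. It opens with a pointer: "A data analytic plan is outlined in the Data Analysis section". It lists the main outcomes (craving, aggression, and subjective, physiological and neuroendocrine reactivity) and then says: "Outcome data will be analyzed using chi-square, ANCOVA, and Poisson regression models". It sets alpha at .05. It mentions neither couples nor repeated measures.

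The unit of randomisation is also worded in two ways. The opening of Section 12.0 names dyads, and the Sample Size Justification counts 50 couples per group. The Randomization paragraph of the same section says "Participants will be randomized to oxytocin or placebo", stratified by gender, and does not mention the couple.

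**The concern.** Both statements are current, declarative text about the same outcomes, and nothing ranks them. In their usual form, chi-square, ANCOVA and Poisson regression treat every person as an independent observation. If both partners always receive the same assignment and tend to respond alike, 100 people in an arm carry less information than 100 unrelated people. An analysis that ignores this reports intervals that are too narrow and p-values that are too small.

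The listed methods in standard form also take one value per person. Table 3 schedules eight sets of VAS, heart rate, blood pressure and cortisol readings per participant, which the Section 12.0 models are built to use.

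A further risk is selection. With two unranked sets of methods, the reported one could be chosen after the results are known, and under couple randomisation the less valid set would tend to give the smaller p-values.

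**Working it through.** **Inputs.** From the Sample Size Justification: SD 1.1, 50 couples (100 people) per group, between-group difference 0.4, stated power 80% at alpha 0.25. From item (11): nominal alpha .05. The within-couple ICC is not given anywhere, so I assume 0.1 to 0.5 and also show 0.

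**The plan's own figure.** For 0.4 units, SD 1.1 and two-sided alpha 0.25, a normal-approximation power calculation gives:
- 92.2% with 100 independent people per arm;
- 74.8% with 50 independent units per arm (each couple counted once, ICC 1).

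The stated 80% lies between the two. It cannot be reproduced without an ICC, and it is not shown to be wrong.

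**Effect of ignoring couples when couples are randomised.** For clusters of two, the variance of the arm difference is (1 + ICC) times the value under independence.
- Naive SE = 1.1 × √(2/100) = 0.156
- Correct SE = 0.156 × √(1 + ICC)
- True type I error of a nominal 5% test = 2 × [1 − Φ(1.96/√(1 + ICC))]

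| Assumed ICC | Correct SE | Naive SE too small by | True type I error |
|---|---|---|---|
| 0 | 0.156 | 0% | 5.0% |
| 0.1 | 0.163 | 5% | 6.2% |
| 0.2 | 0.170 | 9% | 7.4% |
| 0.3 | 0.177 | 12% | 8.6% |
| 0.5 | 0.191 | 18% | 11.0% |

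Example, ICC 0.2: √1.2 = 1.095; 1.96/1.095 = 1.789; two-sided tail area 0.074.

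**Simulation.** With 20,000 simulated trials of 100 couples and no treatment effect, a t-test that ignores couples rejected as follows at nominal 5%:

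| ICC | Couples randomised | Individuals randomised separately within gender |
|---|---|---|
| 0.2 | 7.6% | 4.8% |
| 0.5 | 11.1% | 4.7% |

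The first column agrees with the formula. The second shows that the inflation depends on the couple being the unit of randomisation.

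**Repeated readings.** Table 3 has eight assessment times: minutes 0, 5, 40, 50, 70, 85, 100 and 130. The Taylor Aggression Paradigm (TAP) is run once per participant, and its indices (number of shocks, intensity of the first unprovoked shock, proportion of maximum shocks, average intensity) give one value per person. The repeated-measures objection therefore applies to craving, heart rate, blood pressure and cortisol, but not to the TAP indices.

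**The case against.** The strongest defence is that item (11) is a short summary written for a safety-plan prompt, and that it sends the reader to the analysis section before naming any test. Section 12.0 carries the title of statistical analysis plan. An identity-link model adjusted for baseline is close to ANCOVA, and a log-link count model is close to Poisson regression, so the sentence may be shorthand for the mixed models. Item (11) also never says that partners are treated as independent.

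Much of this stands. It makes Section 12.0 the likely intention, and it lowers the severity. It does not remove the conflict: the pointer does not say which text governs, and chi-square is not shorthand for either of the two models named under Hypothesis 1.

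Three stronger readings are tempting but are not supported.

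- *The trial's error bars will be wrong.* That needs item (11) to be followed in standard form, couples to be the unit, and a positive ICC. None of the three is settled by the documents taken together.
- *The power statement reveals the ICC.* Solving for 80% power gives a design effect of about 1.67, which might be read as an ICC of about 0.67 and a correspondingly larger error rate. The documents state no such value. If 0.4 is rounded from 0.35 to 0.45, the same arithmetic (effective n per arm = 9.6/difference²) allows design effects from about 1.28 up to the maximum of 2 for pairs. An unstated allowance for missing data could also explain the gap.
- *The non-parametric fallback has the same defect.* Section 12.0 says that, should any variables "exhibit significant departures from normality, variable transformations (e.g., logarithmic) or non-parametric approaches will be used, as appropriate". That sentence sits in the paragraph which rules that "all analyses will account for potential within-dyad correlation", so the fallback is already bound to respect couples. No list of permitted methods needs to be imposed.

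**Conclusion.** The conflict is real, and the sentence in item (11) is wrong as written if Section 12.0 is the plan. Its size cannot be fixed from the documents. With couples randomised and the listed methods used in standard form, an assumed ICC of 0.1 to 0.5 makes the naive standard error 5% to 18% too small and raises a nominal 5% test to a true error of about 6% to 11%. At ICC 0 nothing changes, and with partners randomised separately there is little or no inflation. The loss of the serial readings is a separate consequence and does not depend on the ICC.

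This should be corrected before analysis, but it is not a flaw in the design. Section 12.0 already contains a suitable couple-level approach, and neither the sample size nor the data collection is affected.

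**What to change.** 1. In Section 13.0 item (11), replace the sentence listing the three methods with: *Outcomes will be analysed by the mixed models with random couple effects in Section 12.0.*
2. Reconcile the unit of randomisation within Section 12.0, where the opening paragraph names dyads and the Randomization paragraph names participants. State it once, and say how gender stratification works with that unit.

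The cost is two wording changes, with no effect on sample size, visits or procedures. If couples are randomised and partners' outcomes are positively correlated, reported intervals will be wider and p-values larger than the item (11) methods would have given.
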